## INVESTIGATIONAL PLAN SUMMARY

Title:	Evaluation of the Effectiveness, Safety and Tolerability of LevoCept (Levonorgestrel-Releasing Intrauterine System) for Long-Acting Reversible Contraception
Protocol #:	CMDOC-0022 Version 4.0 / 18 October 2017
Device Name:	LevoCept Intrauterine Contraceptive; Levonorgestrel-Releasing Intrauterine System (referred to as LevoCept or Study Device throughout this document)
Study Design:	Prospective, multi-center, single-arm, open-label, Phase II clinical study
Study Purpose:	To evaluate the effectiveness, device placement, safety, and tolerability of LevoCept to support commencing a Phase III Clinical Study
Study Duration:	Subject enrollment will take approximately 5 months. Each subject will be followed for 12 months after device placement for the protocol endpoints, and then every 6 months thereafter for up to 24 additional months for those subjects who wish to continue study device use.
Enrollment:	Up to 250 subjects will be consented, screened and have LevoCept placed, with a goal to have 2240 evaluable cycles at 12 months. It is planned that 225 of the 250 subjects will be within the 18-35 year age range, with a total of 2015 evaluable cycles. The remaining 25 subjects will be within the 36-40 year age range.
Investigational Site Information:	This study will be conducted at approximately 16 centers in the U.S.
Follow-up:	
Physical assessment (office visit) will occur at weeks 6, 13, 26 and 52 after placement, with monthly contact. For those subjects who wish to continue study device use after 12 months, follow-up office visits will occur every 6 months with contact at the end of each 28-day cycle beginning after the 52-week visit. Additional visits will be conducted if necessary for safety issues.
 
Follow-up after early study device removal:
 
Subjects requesting LevoCept removal to become pregnant will be followed for either; six (6) months, until they decide to no longer try to conceive or they become pregnant, whichever comes first. All subjects in whom LevoCept is removed, for any reason, will be required to use an alternative contraceptive for the first two weeks following removal. Hormonal contraceptive pills will be reimbursed by the sponsor as a contraceptive option during this

time unless the subject has a MEC category 4 condition precluding their use.

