#### **4.5 LevoCept Dosage Modification**

All subjects will receive the same LevoCept device and dosage. No Study Devices will be replaced if an expulsion or removal occurs.

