4.2 Safety and other Variables

Safety and other measures are study device placement, safety, and tolerability.

1. Placement success

Device successfully deployed at first try rate is defined as the percentage of the number of subjects with successful deployment at first attempt among the total number of subjects with first attempt.

Device successfully deployed at second try rate is defined as the percentage of the number of subjects with successful deployment at second attempt among the total number of subjects with second attempt.

Device successfully deployed rate is defined as the percentage of the number of subjects with successful deployment in either first or second attempt among the total number of subjects enrolled.

2. Ease of placement

Five categories of how easy the device placement have been collected: Very easy, Easy, Neither Easy nor Hard, Hard and Very Hard.

Five categories of device placement pain as rated by the subject: No Pain, Some Pain, Painful, Moderately Painful and Very Painful.

Question of insertions requiring mechanical cervical dilatation has been collected.

3. Adverse events

All Adverse Events (AEs) will be coded from verbatim text to PTs and grouped by system organ class (SOC) using the Medical Dictionary for Regulatory Activities (MedDRA) (version 17.0). AEs will be collected from the beginning of the study device placement procedure through to study exit. Pre-existing conditions that worsen during a study are to be reported as AEs.

Throughout the study, all AEs will be evaluated by the investigator and noted in the AE section of the CRF.

AEs will be classified as not related, unlikely related, probably related, or related events when considering their relationship to study device, study device placement/removal procedure. Also, AEs will be classified as mild, moderate, severe when considering their severity. If the severity or relationship of an AE is missing, the severity/relationship will be coded as severe, related, respectively, i.e. worst case scenario.

Treatment-emergent AEs (TEAEs): AEs that develop or that worsen in intensity during or after the exposure to the study device.

See Appendix 1 for handling of partial dates for AEs. If it cannot be determined whether the AE is treatment emergent due to a partial onset date then it will be counted as such.

Other AE variables include study device related AEs, AEs leading to study withdrawal, AEs leading to deaths, life threatening AEs, and serious AEs (SAEs).

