5.3 Safety Population

The safety analysis population will include all enrolled subjects who underwent a successful study device placement procedure.

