5.4 Extension Analysis Population

Extension subjects are those who agree to continue study device use after 12 months, up to 2 additional years for a total maximum of 3 years.

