6.2.9.1 Adverse Events

Number of AEs will be summarised by SOC and/or PT for the following categories of TEAEs: all AEs, SAEs, AEs related to study device, AEs related to study device placement/removal procedure, AEs leading to death, AEs leading to study device removal and AEs as primary reason for exiting study. Patients with more than one occurrence of the same SOC (PT) will be counted only once within the SOC (PT) categorisation.

AEs will also be summarised similarly by severity (i.e. mild, moderate, severe), relationship to study device (i.e. not related, unlikely related, probably related, related), relationship to placement/removal procedure (i.e. not related, unlikely related, probably related, related) and onset time frame (i.e. 0-3 months, >3-6 months, >6-12 months, >12 months). Should a subject experience more than one occurrence of the same SOC (PT), the subject's worst occurrence (worst intensity/most related causality) will be retained in the tabulation.

All AEs, including AEs that started prior to the study device placement, will be presented in data listings. In addition, separate listings of all SAEs, AEs related to study device, AEs related to study device placement/removal procedure, AEs leading to death, AEs leading to study device removal and AEs as primary reason for exiting study will be provided. In case of any AEs reported from study device insertion failure subjects, selected AE tables will be repeated for all enrolled subjects for all AEs.

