Program Location: \\xx\xxx\xxx\xxx\xxxxxx\xxxxxxxxxxxxxxxx\xxxx\xxxxx.sas

date

time

CONFIDENTIAL

Sebela Pharmaceuticals Development LLC
CMDOC-0022

Page x of y

Table 14.3.1.12
Treatment-Emergent Adverse Events by Preferred Term by Onset Time Frame for the First Year (Safety Population)

Preferred Term	Events (N=xx) n				Subjects (N=xx) n(%)			
	0 – 3 Months	>3 – 6 Months	>6 – 12 Months	Overall	0 – 3 Months	>3 – 6 Months	>6 – 12 Months	Overall
Number (%) of subjects with any AEs	n	n	n	n	n (%)	n (%)	n (%)	n (%)
Preferred Term 1	n	n	n	n	n (%)	n (%)	n (%)	n (%)
Preferred Term 2	n	n	n	n	n (%)	n (%)	n (%)	n (%)
Preferred Term 3	n	n	n	n	n (%)	n (%)	n (%)	n (%)
Preferred Term 4	n	n	n	n	n (%)	n (%)	n (%)	n (%)

Note: Only treatment-emergent AEs are summarised in this table. An AE that started on or after the date/time of study device placement, or an AE with an unknown/not reported onset date/time is defined as a TEAE.

Note: The denominator for the percentages is the number of subjects (N) in the safety population.

Note: AEs are coded using MedDRA v xxx.

Note: Preferred terms are listed in descending order based on the overall subjects column.

Note: At each level of summation (overall, time frame, preferred term), subjects reporting more than one AE are counted only once.

AE=adverse event; MedDRA = Medical Dictionary for Regulatory Activities; TEAE = Treatment-Emergent Adverse Event.

Reference: Listing xxx.

Program Location: \\xx\xxx\xxx\xxx\xxxxxx\xxxxxxxxxxxxxxxx\xxxx\xxxxx.sas

date

time

CONFIDENTIAL

Sebela Pharmaceuticals Development LLC
CMDOC-0022

Page x of y

Table 14.3.1.13
Treatment-Emergent Adverse Events by Preferred Term by Onset Time Frame (Safety Population)

Preferred Term	Events (N=xx) n					Subjects (N=xx) n(%)				
	0 – 3 Months	>3 – 6 Months	>6 – 12 Months	>12 Months	Overall	0 – 3 Months	>3 – 6 Months	>6 – 12 Months	>12 Months	Overall
Number (%) of subjects with any AEs	n	n	n	n	n	n (%)	n (%)	n (%)	n (%)	n (%)
Preferred Term 1	n	n	n	n	n	n (%)	n (%)	n (%)	n (%)	n (%)
Preferred Term 2	n	n	n	n	n	n (%)	n (%)	n (%)	n (%)	n (%)
Preferred Term 3	n	n	n	n	n	n (%)	n (%)	n (%)	n (%)	n (%)
Preferred Term 4	n	n	n	n	n	n (%)	n (%)	n (%)	n (%)	n (%)

Note: Only treatment-emergent AEs are summarised in this table. An AE that started on or after the date/time of study device placement, or an AE with an unknown/not reported onset date/time is defined as a TEAE.

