Note: The denominator for the percentages is the number of subjects (N) in the safety population.

Note: AEs are coded using MedDRA v xxx.

Note: Preferred terms are listed in descending order based on the overall subjects column.

Note: At each level of summation (overall, time frame, preferred term), subjects reporting more than one AE are counted only once.

AE=adverse event; MedDRA = Medical Dictionary for Regulatory Activities; TEAE = Treatment-Emergent Adverse Event.

Reference: Listing xxx.

Program Location: \\xx\xxx\xxx\xxx\xxxxxx\xxxxxxxxxxxxxxxx\xxxx\xxxxx.sas

date

time

Table 14.3.2.1
Deaths (All Enrolled Subjects)

Subject ID	Date of Death	Cause of Death	Primary Adverse Event # ^[1]	Comment
xxx-xxx	YYYY-MM-DD	SAE	xx	xxxxx
xxx-xxx	YYYY-MM-DD	Unknown		xxx
xxx-xxx	YYYY-MM-DD	Other, specify		xxx

[1] If subject's death was due to a SAE, provide primary Adverse Event.

Program Location: \\xx\xxx\xxx\xxx\xxxxxx\xxxxxxxxxxxxxxxx\xxxx\xxxxx.sas date time

Sebela Pharmaceuticals Development LLC
CMDOC-0022

Page x of y

Table 14.3.2.2
Serious Adverse Events (All Enrolled Subjects)

Programmer notes
This listing will follow a similar format as Listing 16.2.7.1

Table 14.3.2.3
Adverse Events as Primary Reason for Exiting Study (All Enrolled Subjects)

Programmer notes:
The following listings will follow a similar format as Listing 16.2.7.1:

CONFIDENTIAL

Sebela Pharmaceuticals Development LLC
CMDOC-0022

Page x of y

Table 14.3.5.1
Treatment Exposure (All Enrolled Subjects)

	All Subjects (N=xx)
Device Deployed at First Attempt	
Yes	n (%)
No	n (%)
If No, Made a Second Attempt	
n	n
Yes	n (%)
No	n (%)
Device Deployed at Second Attempt	
n	n
Yes	n (%)
No	n (%)
Device Deployed in either Attempt	
Yes	n (%)
No	n (%)
Number of Cycles with Device Use	
n	xx
Mean	xx.x
SD	xx.xx
Median	xx.x
Min	xx
Max	xx

Note: Percentages are based on the number of subjects specified in the column header, i.e. N, unless small n is specified for each category.

Reference: Listing xxx.

Program Location: \\xx\xxx\xxx\xxx\xxxxxx\xxxxxxxxxxxxxxxx\xxxx\xxxxx.sas

date

time

CONFIDENTIAL

Sebela Pharmaceuticals Development LLC
CMDOC-0022

Page x of y

Table 14.3.5.2
Device Placement and Subject Pain During the Procedure (All Enrolled Subjects)

	All Subjects (N=xx) n (%)
Difficulties with the Device Deployment	
n	n
Yes	n (%)
No	n (%)
Ease of Device Placement	
n	n
Very easy	n (%)
Easy	n (%)
Neither easy nor hard	n (%)
Hard	n (%)
Very hard	n (%)
Device Placement Pain	
n	n
No Pain	n (%)

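### Adverse-event percentages by onset window divide by every woman fitted, so late-window figures understate the risk among women still followed

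*SAP*

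**What the plan says.** SAP section 6.2.9.1 asks for adverse events by "onset time frame (i.e. 0-3 months, >3-6 months, >6-12 months, >12 months") and names no denominator for the separate windows. The table shells supply one. The footnote to Table 14.3.1.13 reads "The denominator for the percentages is the number of subjects (N) in the safety population". The same footnote stands under the first-year Table 14.3.1.12 and under Table 14.3.1.1.1, which splits onset into rows from Day 1 to beyond Day 912. Table 14.3.1.1.2 repeats that layout for all enrolled women.

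Four other provisions determine who can appear in a late window:

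- SAP 5.3: "The safety analysis population will include all enrolled subjects who underwent a successful study device placement procedure". Length of follow-up plays no part.
- SAP 4.2: "AEs will be collected from the beginning of the study device placement procedure through to study exit".
- Protocol 4.5: "No Study Devices will be replaced if an expulsion or removal occurs".
- Follow-up after month 12 is optional. The Investigational Plan Summary provides "up to 24 additional months for those subjects who wish to continue study device use", and SAP 5.4 says "Extension subjects are those who agree to continue study device use after 12 months".

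**The concern.** An onset table is read to see whether the risk of an event falls or persists with longer use. A woman who exits at month 4 has no routine adverse-event collection afterwards. She still sits in the denominators of the >6-12 and >12 month columns as if she had been watched and found free of events. The later the window, the more such women there are.

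The window lengths cause a second problem. A column covering up to 24 months collects more events than one covering 3 months, even at a constant risk.

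The study is meant to supply safety data to support Phase III (Protocol section 5), so how events behave beyond the first year is of real interest.

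**Working it through.** The documents state no adverse-event percentage, so there is no printed figure to reproduce. The check is arithmetic on the definition.

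**Inputs**

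- N = 250: the planned maximum number of placements (Investigational Plan Summary), used as an illustrative safety population.
- Mean use in year 1 of 10 cycles per subject (Protocol, Sample Size), in a year of 13 cycles (Protocol 20.6). The protocol calls these cycles evaluable, but its total is recovered only if the 9.2% exclusion is taken off afterwards: 225 × 0.99 × 10 × 0.908 = 2,022.6, against 2,015 stated. The 10 is therefore read here as cycles of use.
- f, the share still followed at the start of a window: not in the documents, so assumed.
- n = 15 women with an event after month 12: illustrative.

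**Identity**

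Printed percentage = n / N. Percentage among women followed = n / (f × N). So printed = f × percentage among women followed, and the understatement factor is 1/f. The factor does not depend on N or n.

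**Share followed at month 12, if mean use is 10 of 13 cycles**

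| Loss pattern (assumed) | f | 1/f | 15 women as % of those followed |
|---|---|---|---|
| All loss at the start | 10/13 = 0.77 | 1.3 | 15/192.3 = 7.8% |
| Constant hazard | (1 − f)/(−ln f) = 10/13, so f ≈ 0.58 | 1.7 | 15/145 = 10.3% |
| Linear loss | 2 × 10/13 − 1 = 0.54 | 1.9 | 15/134.6 = 11.1% |

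The table as planned prints 15/250 = 6.0% in all three cases. Because the share followed essentially only falls, it cannot exceed its year-1 average at month 12. Under the planning assumption, 0.77 is therefore a ceiling and 1.3 a minimum factor.

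**Earlier windows, constant hazard**

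f at month 3 = 0.58^(1/4) = 0.87, factor 1.15. f at month 6 = 0.58^(1/2) = 0.76, factor 1.31. The 0-3 month window starts with everyone and is least affected.

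**Effect of window length**

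Take the same constant loss, λ = −ln(0.58)/12 = 0.0454 per month, continued to month 36. Woman-months per woman fitted in a window from a to b are (e^(−λa) − e^(−λb))/λ. The share followed at months 3, 6, 12 and 36 is 0.873, 0.762, 0.580 and 0.195.

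- 0-3 months: (1 − 0.873)/0.0454 = 2.8
- >3-6 months: (0.873 − 0.762)/0.0454 = 2.4
- >6-12 months: (0.762 − 0.580)/0.0454 = 4.0
- >12 months: (0.580 − 0.195)/0.0454 = 8.5

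For a rare event with constant risk, the >12 month column would be about three times the first (8.5/2.8 = 3.0), although its denominator is too large. In Table 14.3.1.1.1, the rows from Day 183 to Day 911 are of nearly equal length (182 or 183 days). There, loss alone would make each row about 0.58^(1/2) = 0.76 of the one before.

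**The case against.** The strongest defence is that the tables show a disclosed crude proportion: of all women fitted, how many had an event starting in this window? The footnote says so, event counts stand beside the percentages, and SAP 6.2.9 plans no inferential safety analysis. That stands for the Overall column, where n/N is the right figure. It does not rescue the window columns, which serve only to compare periods.

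A second defence is that the missing counts are available elsewhere. Table 14.1.3 gives women at each visit, Table 14.1.1 gives the number entering the extension, and the listings give days on device and adverse-event study days. A reader could rebuild approximate figures, but the SAP plans no number at risk per window and no exposure-adjusted rate. Cycles of use are summarised overall only (Table 14.3.5.1).

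A reader might also draw two stronger conclusions that the documents do not support:

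- **That the late columns must shrink and suggest improving tolerability.** The unequal windows push the other way. On the constant-risk illustration, the >12 month column is the largest. Even with only 40% followed past month 12 and the same later loss, it would hold 0.40 × (1 − 0.195/0.580)/0.0454 ≈ 5.8 woman-months, about double the first window.
- **That late percentages are understated 2.5-fold (15 women being 15% of those followed).** That needs 40% continuation, below the 54% to 77% obtained from the planned mean use. Women declining the extension could lower the share, but neither document gives a figure.

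A third objection concerns the remedy and is sound. Dividing by women with the device in place would not match the numerator, because SAP 4.2 counts events during or after exposure. Table 14.3.1.1.2 also includes women whose insertion failed.

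**Conclusion.** The point holds as a fault of presentation in the onset-window percentages. Their downward direction, relative to risk among women still followed, follows from the documents whenever anyone has left before the window opens. The size is conditional: a factor of about 1.3 to 1.9 beyond 12 months, if mean use is 10 of 13 cycles and loss follows one of the simple patterns above. Actual retention is not stated.

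The columns cannot be compared with each other, and the net visible trend may rise or fall. The one-year analysis, which SAP section 7 says uses the same analyses as the final report, is more exposed. Follow-up beyond month 12 will then be partial, while the >12 month column still divides by all women fitted.

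The primary effectiveness estimate and the overall adverse-event incidence are not affected. This is a cheap improvement to interpretability and does not show the safety analysis to be invalid.

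**What to change.** - In Tables 14.3.1.12 and 14.3.1.13 and the onset rows of 14.3.1.1.1, show for each window the number of women still under follow-up at its start, and use that number as the window's denominator.
- Add events per 100 woman-years of follow-up within each window. The starting count alone corrects neither for unequal window length nor for loss during a window of up to 24 months.
- Keep N of the safety population for Overall, and reword the footnotes to name both denominators.
- In Table 14.3.1.1.2, apply the same rule to all enrolled women under follow-up at the start of the window, so that women with failed insertion are in both numerator and denominator. State the start date used for them, since SAP 1.2 defines Day 1 by successful deployment.

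The SAP already uses period-specific denominators elsewhere: the dyspareunia shift tables divide by women with data at the cycle concerned.

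The cost is one derived count and one rate per window, plus footnote edits, with no new data collection. The downside for the sponsor is that late percentages will look less favourable.

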16.2.7.2 Adverse Events Related to Study Device (All Enrolled Subjects)

16.2.7.3 Adverse Events Related to Study Device Placement/Removal Procedure (All Enrolled Subjects)

16.2.7.4 Adverse Events Leading to Study Device Removal (All Enrolled Subjects)

16.2.7.5 Adverse Events Leading to Death (All Enrolled Subjects)

Listing 16.2.8.1
Subject Diary (All Enrolled Subjects)
Part 1 of 2

CONFIDENTIAL

Question ID	Question Description	Responses Description
QS1	Did you have a period (Menses) or other vaginal bleeding today?	None - None(No bleeding or spotting); Spotting - Spotting(minimal bleeding, no sanitary products required); Light Bleeding - Light Bleeding(pad, liner, or tampon used); Medium Bleeding - Medium Bleeding(pad, liner, or tampon used); Heavy Bleeding - Heavy Bleeding(pad, liner, or tampon used).
QS2	If vaginal bleeding occurred, was the flow today heavier than when you are not using hormones?	Yes; No.
QS3	Do you have vaginal intercourse today?	Yes; No.
QS4	If you have vaginal intercourse, did you experience pain during intercourse?	No Pain; Some Pain; Painful; Moderately Painful; Very Painful; Not Applicable.
QS5	If you had pain with intercourse, was the pain worse than before IUD insertion?	Yes; No.
QS6	If you have vaginal intercourse, did you use any additional birth control methods?	Yes; No.
QS7	If additional birth control methods were used, please mark all that apply:	Hormonal contraception (e.g., pill, patches, ring); Emergency contraception (e.g., Plan B, Ella); Female barrier (e.g., condom, Spermicide, cap); Male condom Alone; Male condom with Spermicide; Withdrawal; Other(specify).
QS8	Have you experienced any menstrual pain or cramping?	None; Mild; Moderate; Severe.
QS9	If pain or cramping occurred, was the cramping worse than when you are not using hormones?	Yes; No.
QS10	Did the LevoCept device expel?	Yes; No; Suspected.

CONFIDENTIAL

Sebela Pharmaceuticals Development LLC
CMDOC-0022

Page x of y

Listing 16.2.8.1
Subject Diary (All Enrolled Subjects)
Part 2 of 2

Subject ID	Date	Sequence #	Cycle #	Day #	QS1	QS2	QS3	QS4	QS5	QS6	QS7	QS8	QS9	QS10
xxx-xxx	YYYY-MM-DD	xx	xx	xx	None		Yes	No Pain	Yes	Yes	Hormonal contraception	None	Yes	Yes
	YYYY-MM-DD	xx	xx	xx	Spotting		Yes	Some Pain	Yes	Yes	Emergency contraception	Mild	Yes	Yes
	YYYY-MM-DD	xx	xx	xx	Light Bleeding	Yes	Yes	Painful	Yes	Yes	Female barrier	Moderate	Yes	Yes
	YYYY-MM-DD	xx	xx	xx	Medium Bleeding	No	No	Not Applicable	Yes	Yes	Male condom Alone	Severe	Yes	Yes
	YYYY-MM-DD	xx	xx	xx	Heavy Bleeding	Yes	No	Not Applicable	Yes	Yes	Male condom with Spermicide		Yes	Yes
	YYYY-MM-DD	xx	xx	xx	None		Yes	No Pain	Yes	Yes	Withdrawal			
	YYYY-MM-DD	xx	xx	xx	None		Yes	Moderately Painful	No	No	Other, specify			
	YYYY-MM-DD	xx	xx	xx	None			Very Painful	No	No				
xxx-xxx					None						Hormonal contraception/			
	YYYY-MM-DD	xx	xx	xx			Yes	No Pain	Yes	Yes	Other, specify	None	No	No
					Spotting						Female barrier/			
	YYYY-MM-DD	xx	xx	xx			Yes	No Pain	Yes	Yes	Male condom with Spermicide	Mild	No	No
Program Location: \\xx\xxx\xxx\xxx\xxxxxx\xxxxxxxxxxxxxxxxxxx\xxxx\xxxxx.sas							date	time						

CONFIDENTIAL

Sebela Pharmaceuticals Development LLC
CMDOC-0022

Page x of y

Listing 16.2.8.2
Subject Missed Diary Review (All Enrolled Subjects)

Subject ID	At least one Diary Missed	Date of Missed	Sequence #	CRF Cycle #	Cycle #	Day #	Vaginal intercourse	Additional Birth Control [1]	Pain[2]	Pain Worse[3]
xxx-xxx	Yes	YYYY-MM-DD	xx	xx	xx	xx	Yes	Yes	No Pain	Yes
	Yes	YYYY-MM-DD	xx	xx	xx	xx	Yes	No	Some Pain	No
	Yes	YYYY-MM-DD	xx	xx	xx	xx	Yes	Yes	Painful	Yes
xxx-xxx	Yes	YYYY-MM-DD	xx	xx	xx	xx	Yes	Yes	Moderately Painful	Yes
	Yes	YYYY-MM-DD	xx	xx	xx	xx	No		Not Applicable	No
	Yes	YYYY-MM-DD	xx	xx	xx	xx	Yes	Yes	Very Painful	Yes
xxx-xxx	No									

[1] If yes, did the subject use any additional birth control methods?

[2] Did the subject experience pain during intercourse?

[3] If the subject experienced pain during intercourse, was the pain worse than before IUD insertion

Program Location: \\xx\xxx\xxx\xxx\xxxxxx\xxxxxxxxxxxxxxxx\xxxx\xxxxx.sas date time

CONFIDENTIAL

Sebelo Pharmaceuticals Development LLC
CMDOC-0022

Page x of y

Listing 16.2.8.3
Monthly Phone Contact (All Enrolled Subjects)

Subject ID	Contact Conducted	Date of Contact	Cycle #	Intercourse[1]	Additional Birth Control [2]	Medications[3]	Adverse Events[4]	Resolve or Change[5]
xxx-xxx	Yes	YYYY-MM-DD	xx	Yes	Yes	Yes	Yes	Yes
		YYYY-MM-DD	xx	No	No	No	No	No
		YYYY-MM-DD	xx	Yes	Yes	Yes	Yes	Yes
xxx-xxx	No							
xxx-xxx	Yes	YYYY-MM-DD	xx	Yes	Yes	Yes	Yes	Yes
		YYYY-MM-DD	xx	No	No	No	No	No
		YYYY-MM-DD	xx	Yes	Yes	Yes	Yes	Yes

[1] Did subject have intercourse at least one time during the previous Cycle?

[2] Did the subject use any additional forms of birth control or emergency contraception during the previous Cycle?

[3] Has subject taken any medications since the last contact?

[4] Did subject experience any Adverse Events since the last contact?

[5] Did any prior Adverse Events resolve or change since the last contact?

Program Location: \\xx\xxx\xxx\xxx\xxxxxx\xxxxxxxxxxxxxxxx\xxxx\xxxxx.sas

date

time

CONFIDENTIAL

Sebela Pharmaceuticals Development LLC
CMDOC-0022

Page x of y

Listing 16.2.8.4
Subject Study Visits (All Enrolled Subjects)

Subject ID	Visit	Date	Not Done	If Not Done, Specify Reason
xxx-xxx	xxxxx xxxxx	YYYY-MM-DD	Yes	Subject Discontinued Prior to this Visit
xxx-xxx	xxxxx xxxxx	YYYY-MM-DD	Yes	Other, Specify
xxx-xxx	xxxxx xxxxx	YYYY-MM-DD YYYY-MM-DD		

Program Location: \\xx\xxx\xxx\xxx\xxxxxx\xxxxxxxxxxxxxxxx\xxxx\xxxxx.sas

date

time

CONFIDENTIAL

Sebela Pharmaceuticals Development LLC
CMDOC-0022

Page x of y

Listing 16.2.8.5
Long Term Follow-up (Extension Population)

Subject ID	Visit	Date	Additional Birth Control [1]	Vaginal Intercourse [2]	Frequency[3]
xxx-xxx	xxxxx	YYYY-MM-DD	Yes	No	Several times a month
	xxxxx	YYYY-MM-DD	Yes	Yes	
xxx-xxx	xxxxx	YYYY-MM-DD	Yes	Yes	Once or twice a week
	xxxxx	YYYY-MM-DD	Yes	Yes	Several times a week
xxx-xxx	xxxxx	YYYY-MM-DD	Yes	Yes	Once a month or less
	xxxxx	YYYY-MM-DD	Yes	Yes	At least once a day

[1] Did subject use additional birth control in the past 6 months?

[2] Did subject have vaginal intercourse at least once since last visit?

[3] If Yes, how often did the subject have vaginal intercourse in the past 6 months?

Program Location: \\x\xxx\xxx\xxx\xxxxxx\xxxxxxxxxxxxxxxx\xxxx\xxxxx.sas

date

time

Programmer notes: Date is not shown on this form, recorded on VISIT form.

CONFIDENTIAL

Sebela Pharmaceuticals Development LLC
CMDOC-0022

Page x of y

Listing 16.2.9.1
Height (All Enrolled Subjects)

Subject ID	Visit	Measured	Date of Measurement	Height (cm)
xxx-xxx	xxxxx	Yes	YYYY-MM-DD	xx.x
xxx-xxx	xxxxx	Yes	YYYY-MM-DD	xx.x

Program Location: \\xx\xxx\xxx\xxx\xxxxxx\xxxxxxxxxxxxxxxx\xxxx\xxxxx.sas date time

CONFIDENTIAL

Sebela Pharmaceuticals Development LLC
CMDOC-0022

Page x of y

Listing 16.2.9.2 Vital Signs (All Enrolled Subjects)

Subject ID	Visit	Collected	Assessment Date	Heart Rate (bpm)	Respiration (breaths/min)	SBP (mmHg)	DBP (mmHg)	Temperature (F)	Weight (kg)	BMI (kg/m2)	BMI category[1]
xxx-xxx	xxxxx	Yes	YYYY-MM-DD	xx*	xx*	xx*	xx*	xx*	xx.x*	xx.x*	Underweight
	xxxxx	Yes	YYYY-MM-DD	xx	xx	xx	xx	xx	xx.x	xx.x	Normal
xxx-xxx	xxxxx	Yes	YYYY-MM-DD	xx*	xx*	xx*	xx*	xx*	xx.x*	xx.x*	Overweight
	xxxxx	Yes	YYYY-MM-DD	xx	xx	xx	xx	xx	xx.x	xx.x	Obese

Note: * Baseline value.

[1] BMI categorized by Underweight (< 18.5), Normal (18.5 – 24.9), Overweight (25.0 – 29.9), and Obese (≥ 30.0).

DBP = Diastolic Blood Pressure; SBP = Systolic Blood Pressure.

Program Location: \\xx\xxx\xxx\xxx\xxxxxx\xxxxxxxxxxxxxxxx\xxxx\xxxxx.sas

date

time

CONFIDENTIAL

Sebela Pharmaceuticals Development LLC
CMDOC-0022

Page x of y

Listing 16.2.9.3
Vital Signs - Change from Baseline Results (All Enrolled Subjects)
Part 1 of 2

Subject ID	Visit	Collected	Assessment Date	Heart Rate (bpm)		SBP (mmHg)		DBP (mmHg)	
				Result	Change from Baseline	Result	Change from Baseline	Result	Change from Baseline
xxx-xxx	xxxxx	Yes	YYYY-MM-DD	xx*		xx*		xx.x*	
	xxxxx	Yes	YYYY-MM-DD	xx		xx	xx	xx.x	xx
xxx-xxx	xxxxx	Yes	YYYY-MM-DD	xx *		xx*		xx.x*	
	xxxxx	Yes	YYYY-MM-DD	xx		xx	xx	xx.x	xx

Note: * Baseline value.

DBP = Diastolic Blood Pressure; SBP = Systolic Blood Pressure.

Program Location: \\xx\xxx\xxx\xxx\xxxxxx\xxxxxxxxxxxxxxxx\xxxx\xxxxx.sas

date

time

CONFIDENTIAL

Sebela Pharmaceuticals Development LLC
CMDOC-0022

Page x of y

Listing 16.2.9.3
Vital Signs - Change from Baseline Results (All Enrolled Subjects)
Part 2 of 2

Subject ID	Visit	Collected	Assessment Date	Weight (kg)		BMI (kg/m2)	
				Result	Change from Baseline	Result	Change from Baseline
xxx-xxx	xxxxx	Yes	YYYY-MM-DD	xx.x*		xx.x*	
	xxxxx	Yes	YYYY-MM-DD	xx.x	xx	xx.x	xx
xxx-xxx	xxxxx	Yes	YYYY-MM-DD	xx.x*		xx.x*	
	xxxxx	Yes	YYYY-MM-DD	xx.x	xx	xx.x	xx

Note: * Baseline value.

DBP = Diastolic Blood Pressure; SBP = Systolic Blood Pressure.

Program Location: \\xx\xxx\xxx\xxx\xxxxxx\xxxxxxxxxxxxxxxx\xxxx\xxxxx.sas

date

time

CONFIDENTIAL

Sebela Pharmaceuticals Development LLC
CMDOC-0022

Page x of y

Listing 16.2.9.4
Physical Examination (All Enrolled Subjects)

Subject ID	Visit	Performed	Date of Examination	Any Clinically Significant Abnormalities
xxx-xxx	xxxxx	Yes	YYYY-MM-DD	No
	xxxxx	Yes	YYYY-MM-DD	Yes
xxx-xxx	xxxxx	Yes	YYYY-MM-DD	No
	xxxxx	Yes	YYYY-MM-DD	No

Program Location: \\xx\xxx\xxx\xxx\xxxxxx\xxxxxxxxxxxxxxxxxxxxxx\xxxx\xxxxx.sas date time

CONFIDENTIAL

Sebela Pharmaceuticals Development LLC
CMDOC-0022

Page x of y

Listing 16.2.9.5
Pelvic Examination (All Enrolled Subjects)

Subject ID	Visit	Performed	Date of Examination	Any Clinically Significant Abnormalities
xxx-xxx	xxxxx	Yes	YYYY-MM-DD	No
	xxxxx	Yes	YYYY-MM-DD	Yes
xxx-xxx	xxxxx	Yes	YYYY-MM-DD	No
	xxxxx	Yes	YYYY-MM-DD	No

Program Location: \\xx\xxx\xxx\xxx\xxxxxx\xxxxxxxxxxxxxxxxxxxxxx\xxxx\xxxxx.sas date time
